OVERALL IMPACT, SIGNIFICANCE, INVESTIGATOR(S) & INNOVATION: *inclusion/exclusion criteria not in grant (R1&R2).* We apologize for placing too much of that info in Human Subjects. It is now in section D.2 (and Human Subjects [1.a.]) *Unclear how nonadherence due to smartphone service loss will be handled (R1):* In our feasibility trials we observed high BP monitoring adherence via phone app (~88%), nonadherence tended to occur when cellular service was disrupted. We budgeted for 40% to receive a smart phone or data package to cover phone or service loss during the trial (in D.4.) *Justify relatively limited age range (21-59 yrs) (R1):* We are recruiting AAs from a federally qualified health center (FQHC) with sole diagnosis of HTN (n=2,619; mean age ~45.3 yrs). Majority of those ≥ 60 had multiple comorbidities & JNC8 BP control goals differ for patients <60 vs ≥60. *Concern PI may not have time (25%FTE) to devote to project (R1):* Within 2 mos of start date for this grant, [name] will be covered 50% FTE on grants (R21 & RO1 will have expired; see bio). He has a long track record of running successful concurrent trials. An experienced full time project manager has been added, [name]. *Consider adding someone with usability testing background (R1):* [name] is a consultant with expertise in user centered, iterative design in web/app programs including use of various usability evaluation tactics (e.g., expert heuristic & end user think aloud evals, questionnaires; see bio & letter). *SMASH not highly innovative, been used in other patient groups(R1):* Our patient centered design revealed significant heterogeneity of influence of cultural heritage/acclimation and numeracy of chronic diseases (single vs multi-morbidities) upon MA and other health behaviors within & across ethnic groups. The mHealth program tailored to Hispanics is not culturally attuned for AAs. Our mHealth work with AA renal transplant patients with HTN, diabetes, etc. led to efforts to address poor MA before multi-morbidities develop. Our long-term goal is to prevent common events (e.g., stroke, heart attack) & slow progression of common comorbidities (e.g., chronic kidney disease, diabetes) due to uncontrolled HTN. SMASH for transplant patients required ~2 years of changes to become salient to AAs with solely uncontrolled HTN. We found those with only HTN often have greater MA problems (in C.1.3) & to be more challenging to establish sustained regimen adherence compared to HTNs with multi-morbidities. Experiences during trials & post trial interviews led to an iterative process of identifying highly salient motivational factors (values, beliefs, goals) not needed with multi-morbidity transplant patients (in C.1.5.) Others have observed similar challenges with single vs multi-morbidity HTN patients (in A.2.) This program (nor any earlier iteration) has not been nor is being tested using a fully powered RCT, much less within a low-income population & health system (i.e., FQHC). *No focus on med nonadherence (MNA) mechanisms besides self-motivation or how other diseases & meds affect HTN MA; no lit review on comorbidities(R2):* We clarified HTNs with comorbidities aren't recruited (in D.2.) Exploratory analyses of MNA mechanisms now include med side effects, stress, depression symptoms, etc. (in D.10.) We added diabetes /CVD risk factor changes (e.g., TC, HgA1c) as exploratory outcomes. Recent trials show some newer HTN meds lower or at least do not increase these risk factors (in A.2.) **APPROACH & ENVIRONMENT:** *Limited description of clinics (R1):* 7 of 8 clinics have similar numbers of AAs with uncontrolled HTN and numbers of primary providers (MD, PA, NP; M=2.4). Lead site has 7.3 providers & generates ~45% of patient encounters (in Facilities & Resources). Clinic (=cluster) in our cluster RCT design will be a random effect in the analytic model & account for clinic site differences (in D.10). *More details on SMASH focus group protocol stratification process (R1):* We will identify 2 groups: 16 MA responders & 16 partial/nonresponders stratified by clinic, age & sex. We will run 3-4 focus groups separately by group classification (in D.7.) *Measures of numeracy, usability & project evaluation needed; SMASH & control condition descriptions a bit vague (R1):* We added measures (in D.6.) & reworded SMASH & SC protocols for clarity (in D5-7.) *No model to guide analytic approach; how will data be integrated to provide cohesive story (R1):* We clarified in D.10 our conceptual model is built upon Self-Determination Theory with competence & autonomous motivation as primary MA mediators. We now include socio-demographic (e.g., age, income) & biobehavioral (e.g., med side effects, stress, sleep quality, etc.) factors as potential moderators & mediators of MA. Those results will guide an integrated causal model using structural equation modeling that will identify key active ingredients of SMASH to guide future refinements.

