Feasibility RCTs: Feedback from AAs with HTN and their health care providers guided development, pilot testing and refinement followed by repeated feasibility RCT testing and refinements of a culturally tailored mHealth MA and BP control program for AAs called Smartphone MA Stops Hypertension (SMASH).²⁰⁻²⁶ SMASH consists of multi-level components: Patient level components include: a) sequential automated reminders from an electronic med tray (blinking light, audio chime, automated call) and b) tailored SMS/voice mail that addresses: 1) motivational and social reinforcement to enhance and sustain adherence; 2) BP monitoring reminders; 3) HTN education and functional health literacy, tips on talking with doctor, etc. Provider level components include: a) weekly summary reports of subjects’ MA and BP levels with JNC8 stepped care guidelines and b) phone alerts to clinic nurse managers when verified out of range BPs occur. Our 3 feasibility trials (3 mos; 6 mos) with AAs with uncontrolled HTN demonstrated high acceptability, self-efficacy for following medical regimen, improved real-time MA, reduced emergency department use and higher percentages reaching JNC8 standard for BP control compared to standard of care (SC) cohorts.²²⁻²⁶ SMASH appears promising but requires further evaluation and refinement. *PA-14-334, Practical Interventions to Improve MA seeks testing of novel, theory guided interventions to improve MNA (self-report & objective indices required) and inclusion of a biological indicator (e.g., BP) expected to be effected by changes in adherence.* We propose to conduct a multi-site cluster efficacy RCT with 192 AAs (21-59 years old) with sole diagnosis of uncontrolled HTN and verified MNA randomly assigned to a 6-month intervention with 12-month follow-up. Evaluations will occur at baseline and months 3, 6, 12, and 18. The central hypothesis is, compared to an enhanced SC group, the SMASH group will exhibit significantly improved MA and resting and 24 hour BP control over the active treatment period (primary endpoint).

Specific aims will assess the efficacy of the SMASH intervention on:

AIM 1) Primary Outcomes: a) Medication adherence: % with electronic monitor-derived adherence scores >0.90; b) BP control: % meeting JNC8 defined BP control (resting BP<140/90 mmHg.)

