D.3.b. MNA Identification Phase: Subjects will be shown how MedMinder™ works and demonstrate proficiency in loading and activating the device. They will be told their doctors will receive summary reports on their med intake patterns. The tray plugs into a standard 110v outlet, has 28 compartments allowing up to 4 dose times per day for 7 days, and is capable of providing escalating reminder signals (described in D.5.a). **Reminder functions will be disabled for the 1-month screening phase.** The nurse manager (or project manager, [name]) and subject will program the MedMinder for dosing times (example of subject's 24-hr MedMinder activity in Appx. 23). Subject will receive written and oral instructions on MA criteria (i.e., all meds taken within 180 min window centered on prescribed dosing time). SMASH app has auto call feature for TACHL service line for technical issues. Time and date stamped opening and closure of the tray's compartments are relayed via GSM wireless cellular transmitter/receiver to MedMinder™ server for processing. The encrypted data are sent to a HIPPA-compliant server database housed in the TACHL center. The MA formula will be used to calculate MA scores.^{22,23,52,121} (see Appx. 2) **Only subjects with MA score < 0.85 over the 4 week screening and whose subsequent resting and 24-hr SBP evaluations reconfirm uncontrolled HTN will be eligible for enrollment into the RCT.** [name] will randomly assign the 8 sites to either SMASH or

enhanced SC conditions.

D.4. Time Table (Table 2) Based on our SMASH trials, we will recruit 16 subjects/mo beginning mo 4 and finish recruiting by mo 15. We will provide a smart phone and/or service plan for ~40 SMASHers we project might lose phones or service plans during the trial.^{20,21,25,27} Post-trial data collection will finish in mo 34. Post study focus groups and subsequent qualitative analyses will end in mo 43. Table 2 presents a timetable for the study.

Activity	Month
Set-up	Mos 1-3
Recruitment	Mos 4-15
Intervention	Mos 5-22
Follow-up	Mos 16-34
Focus Groups	Mos 35-37
Statistical analyses	Mos 23-28
Prep. and Submission of Effectiveness RCT RO1	Mos 36-42
	Mos 43-48
Month	0 2 4 6 8 10 12 14 16 18 20 22 24 26 28 30 32 34 36 38 40 42 44 46 48
Year	1 2 3 4

D.5. SMASH Protocol:

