D.10. Quantitative Analyses: AIM1 Primary outcome measures are % of subjects with >0.90 MA from MedMinder and % within JNC8 clinic resting BP guidelines (<140/90 mmHg). Secondary analyses will assess resting & ambulatory BP levels (e.g., 24-hr, daytime/nighttime BP level changes) & MA indices (i.e., MPR score changes). Intent-to-Treat (ITT) sample analyses will be used along with multiple imputation methods for missing end-of-study outcomes.^{149,150} To assess relationships between intervention outcomes and intervention status (SMASH or SC) at end of the active trial period (6-mo visit, primary endpoint), two-sided Cochran-Mantel-Haentzel chi-square tests for unadjusted differences in proportions will be used. Adjusted differences in proportions at the 6-mo visit will be compared using logistic regression. To assess relationships over time, we will use a generalized linear mixed models (GLMM; generalized estimation equation [GEE]-type models) analytic model with group (SMASH vs SC) & time (3, 6, 12 & 18 months) included as fixed effects and FQHC practice site as a random effect to account for clustering within FQHC practice site/MD.¹⁵¹⁻¹⁵³ In the first set of models, baseline measurement of the dependent variables (e.g., MA or BP levels) will be included as adjustment variable. The test of primary interest is F-test for the treatment x time interaction, which will reflect a difference in change between the 2 groups over the study. If a statistically significant treatment x time

interaction is found, we will obtain odds ratios for SMASH vs SC groups at each of the study time points.

A mixed effects model (MEM) will be used to compare the primary continuous outcome measures (e.g., tray or MPR derived MA scores or BP levels) for the two groups over the study period. Modeling will be carried out as described above. We will estimate resting and 24-hr BP changes and MA (MPR) changes for each subject over the trial (baseline, 3, 6, 12 & 18 months) and the within subject longitudinal trajectories (e.g., slopes) and summarize as the mean longitudinal trajectory within each group. ICCs and variance estimates will be obtained of efficacy outcomes and covariance structure of the longitudinal scores for determination of sample size (and hence adequate power) for a future effectiveness RCT.

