AIM 2 Secondary outcomes of changes in SDT constructs competence & autonomous motivation, % provider adherence to JNC8 guidelines (med changes based upon JNC8 guidelines made in EHR & script delivery within 24 hrs) & 24-hr BP will be assessed using GLMM with these outcomes as separate dependent variables, group as independent variable & primary outcomes (resting BP & MA) & clinical & sociodemographic factors included as adjustment variables. Modeling will be carried out as described above.

AIM 3 Exploratory outcomes of changes in metabolic syndrome /CVD risk factors (TC, LDL, blood glucose and HgA1c) in relation to intervention group with type of med (low vs high dose diuretics; old vs new selective beta1 blockers, etc.) as covariates will be assessed using MEM as described above in AIM1.

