Cost-effectiveness analyses will be run using established methodology for economic evaluation of electronic drug monitoring for MNA.¹⁵⁴ Data will be collected on incremental direct and time cost SMASH program adds to enhanced SC for facilitating MA and BP control. This includes personnel costs for referral & BP/ MA screening, all supplies and equipment used (MedMinders, BP devices, smart phones/ data packages) and costs of additional meds beyond SC. Value of project manager's time will be included in attending to patient assistance calls, verification of out of range BPs, etc. Sensitivity analyses will estimate cost changes related to different types of personnel time needed to perform her tasks. We will define benefits as difference in cost of health services use and lost worked days between SMASH and SC groups. We will compare costs of emergency department (ED), outpatient and hospital visits during the 6-month trial and most importantly, the 12 months following trial completion. We will use estimates from the Healthcare Cost and Utilization Project¹⁴⁵ for ED and hospitalization and the Medical Expenditure Panel Survey¹⁴⁴ (for outpatient and individual out-of-pocket costs) to value healthcare use costs in each group. Thus, healthcare costs will be evaluated at institutional provider, third party payer and individual level and all costs adjusted using inflation adjustment from Bureau of Labor Statistics.¹⁵⁵ We will estimate cost of lost worked days during the 6-mo trial and 12-mo follow-up and reported baseline income. We will assess differences in means, medians and quartiles based on distribution of the variables. As we did in another telehealth project, we will use GLM with appropriate distribution to examine association of SMASH with patient level healthcare costs and patient lost income adjusting for patient demographics and comorbidities.¹⁵⁶ We will conduct sensitivity analyses by estimating different healthcare costs and income models while adjusting for clinical outcomes (e.g., % with JNC8 BP control; % with 24-hr BP control). We will do the same for healthcare utilization and lost workdays using a count model (Poisson or Neg Bin if over dispersion occurs or zero-inflated if many zeros are present). We will perform a comparison of SMASH cost with changes in clinical outcomes to provide cost-effectiveness ratios for clinical outcomes.

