Exploratory Moderator Analyses: Our conceptual model will guide moderator analyses of MA and BP control using logistic regression with >90% MA or BP control at 6 months as dependent variable and the GLMM/GEE model over the entire study (measurement times 3, 6, 12 and 18 months). Modeling will be carried out in a sequential fashion. Initial set of models will first be adjusted for sociodemographics (age, gender, education, marital status, income), autonomous motivation and biobehavioral factors (e.g., stress, sleep quality, depressive symptoms, med side effects, etc.). If needed, models will be further adjusted for new comorbidities (e.g., diabetes) and associated additional meds. Effect modifications of covariates (moderators) will be examined through inclusion of a covariate-by-group (SMASH vs SC) interaction term in the multivariable models.⁶⁷ We are especially interested in the interaction of treatment by gender, as well as SES and autonomous motivation.

Exploratory MNA Mediation Analyses: Potential mediators will be examined individually and subsequently in a multivariable model. Exploratory analyses will follow modifications suggested by MacKinnon, Fairchild and Fritz¹⁵⁷ of the causal steps approach developed by Baron & Kenny.¹⁵⁸ Analyses will be guided by our conceptual model framed upon change scores in SDT constructs (competence & autonomous motivation) followed by MNA mediators identified in the empirical literature including biobehavioral (e.g. stress, med side effects, depression symptoms, sleep quality, perceived disease severity, doctor-patient relationship, quality of life, HTN knowledge/beliefs) and process /uptake features (e.g., opening of motivational/reinforcement messages/education info, BP graph uploads via phone, patient SMASH (or SC) usability and satisfaction scale

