The practice sites will have been randomly assigned to SMASH or SC. The MDs and nurse managers at each site will have received an orientation in the SMASH study and refresher on the JNC8 Guidelines for HTN management. **As in our feasibility trials, the project research technicians responsible for conducting all evaluations will remain blinded to the subjects' status for the entire duration of the study and follow-up.** To help prevent contamination, the SMASH and SC subjects will be reminded by phone the night before study evaluations by [name] and again in clinic by the nurse manager, not to discuss their involvement in the trial with the technicians. Subjects will also be instructed not to discuss their treatment regimen with other individuals excepting those in their household. **The SMASH project manager, [name], will not be directly involved with data collection, as she will be a phone contact for SMASH subjects and will not be blinded.** This same approach was successful in the 6-month FQHC feasibility trial.

Primary clinical outcome variables are 1) fraction of subjects reaching JNC8 guidelines for BP control (i.e., resting BP $< 140/90$ mmHg), and 2) fraction of subjects with medication adherence score > 0.90 , as measured by electronic medication tray. Secondary clinical outcome measures include provider adherence to JNC8 guidelines, as measured by timing of medication changes, % reaching 24-hr ambulatory BP control (BP $< 130/80$ mmHg) and changes in subjects' SDT constructs of competence and autonomous motivation. Exploratory outcome variables will include cost effectiveness, other MA indices (i.e., pharmacy record based medication possession ratio [MPR] and self-report [Morisky scale]) and examination of potential moderators (e.g., gender, age, income, etc.) and mediators (e.g., competence, autonomous motivation, perceived disease severity, med side effects, depressive symptoms, sleep quality, etc.) on MA and BP control. We will also explore impact of SMASH program (i.e., increases in MA) upon changes in physical risk factors of TC, LDL, HgA1c and blood glucose. All data will be evaluated on an intent-to-treat basis.

Inclusion Criteria:

1. 21-59 years old; male or female; African American or Black
2. Prescribed medication(s) only for HTN;
3. Medication possession ratio (MPR) $< .85$ for last 3 months;

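### The Aim 2 models adjust for resting BP and MA with no time point; read literally these are on-trial values, and the group coefficient would not estimate the total effect of assignment.

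*Combined protocol and SAP*

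**What the plan says.** Section D.10, AIM 2, gives one model for the SDT constructs (competence and autonomous motivation), provider adherence to JNC8 and 24-hr BP: a GLMM with "group as independent variable & primary outcomes (resting BP & MA) & clinical & sociodemographic factors included as adjustment variables". It then refers back to the modelling described under AIM 1. The rule there is: "In the first set of models, baseline measurement of the dependent variables (e.g., MA or BP levels) will be included as adjustment variable".

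AIM 1 defines the primary outcomes as binary: MA above 0.90 and resting BP below 140/90 mmHg. Section D.3.b restricts entry: "Only subjects with MA score < 0.85 over the 4 week screening and whose subsequent resting and 24-hr SBP evaluations reconfirm uncontrolled HTN" can be enrolled. Section D.2 puts the SBP limit at 140 mmHg or more.

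The central hypothesis in the Specific Aims is that "the SMASH group will exhibit significantly improved MA and resting and 24 hour BP control over the active treatment period (primary endpoint". The Introduction to the Revised Application says that "our conceptual model is built upon Self-Determination Theory with competence & autonomous motivation as primary MA mediators". The Protection of Human Subjects section (1.a) adds: "All data will be evaluated on an intent-to-treat basis".

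**The concern.** A covariate measured after randomisation and changed by the intervention is not a neutral adjustment. If SMASH raises MA and lowers resting BP, a model that holds their on-trial values fixed asks how the arms differ among patients with the same adherence and the same BP. That is not the effect of being assigned to SMASH.

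The SDT constructs are the most awkward case. The plan treats motivation and competence as causes of adherence, so MA lies downstream of the outcome being tested. Adjusting an outcome for its own consequence biases the group coefficient. For 24-hr BP, resting BP is a close relative of the outcome, and adjusting for it would take out much of the effect being sought.

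At stake is the reading of Aim 2. A real gain in motivation, the mechanism on which SMASH is built, could be reported as small, absent or reversed because SMASH also improved adherence.

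**Working it through.** **1. Which values does the text mean?**
- The AIM 1 baseline rule applies to dependent variables. In AIM 2 these are the SDT scores, provider adherence and 24-hr BP, so the rule does not reach resting BP and MA.
- Entry requires MA below 0.85 and SBP of at least 140 mmHg. At baseline nobody has MA above 0.90 and nobody is below 140/90 mmHg. As defined, both primary outcomes are constants at entry and can vary only on trial.
- Continuous baseline BP and MA do vary and are collected, but AIM 2 does not name them.
- Elsewhere in D.10 the plan does use on-trial covariates. For costs: "We will conduct sensitivity analyses by estimating different healthcare costs and income models while adjusting for clinical outcomes (e.g., % with JNC8 BP control". For moderators: "If needed, models will be further adjusted for new comorbidities (e.g., diabetes) and associated additional meds". The first is labelled sensitivity and the second exploratory. AIM 2 carries neither label.

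**2. The plan's own figure.** D.8 gives 80% power for 0.53 SD in Aims 2 and 3, by an unadjusted t-test. With 88 per arm and the stated ICC of 0.04, the effective n is 88/(1 + 21 × 0.04) = 47.8 per arm. The standard error is √(2/47.8) = 0.204 SD and power is Φ(0.53/0.204 − 1.96), about 74%. Without clustering it is 94%. An ICC of 0.03 with 24 per clinic gives about 81%. The ICC behind that sentence is not stated. This is a separate matter; I use 0.53 SD below only as an effect size.

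**3. SDT constructs with on-trial MA as covariate.** In a linear model with MA as the only covariate,

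adjusted effect = total effect − r × d,

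where r is the within-arm correlation of the outcome with MA, and d is the effect of SMASH on MA in SD units.

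Inputs:
- Total effect 0.53 SD (D.8).
- r = 0.20 for competence against electronic adherence (MASES-R appendix); r = 0.58 for autonomous motivation against adherence (TSRQ appendix). Both come from other samples; using them as within-arm values is an assumption.
- d from D.8: either 10 points with SD 15 (the change-score planning figures), or 28 points with SD 6.2 (the pilot).

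| MA figures | d | r = 0.20 | r = 0.58 |
|---|---|---|---|
| 10 points, SD 15 | 0.667 | 0.53 − 0.133 = 0.40 | 0.53 − 0.387 = 0.14 |
| 28 points, SD 6.2 | 4.52 | 0.53 − 0.903 = −0.37 | not meaningful |

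The sign changes when the MA effect exceeds (0.53/r) × SD. At r = 0.20 that is 39.8 points with SD 15 but 16.4 points with SD 6.2; at r = 0.58 with SD 15 it is 13.7 points. At d = 4.52 the arms barely overlap on MA, so the adjustment is extrapolation. The −0.37 shows that the sign is not fixed; it is not a forecast.

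A simulation with assumed d = 0.8 and r = 0.5 gave 0.54 unadjusted and 0.14 adjusted (formula: 0.53 − 0.40 = 0.13). With a true effect of zero and an unmeasured common cause of MA and the outcome, the adjusted effect was −0.40, so bias can also arise under the null.

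**4. 24-hr BP control.** Take 25% v 55% (the SC pilot rate and the 30-point difference in D.8). Assume the same rates for resting control and latent correlations between resting and 24-hr BP of 0.5, 0.7 and 0.8. In simulation, adjusting a logistic model for on-trial resting control leaves about 20, 16 and 13 points. Adjusting for on-trial resting SBP leaves about 15, 9 and 6.

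**5. Baseline covariates instead.** Randomisation makes d zero in expectation, so the formula returns 0.53 SD. A baseline covariate in the 24-hr simulation returns 30 points.

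Provider adherence is not quantified; neither direction nor size can be argued from the documents.

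**The case against.** The strongest reply is that this is loose wording for baseline adjustment. AIM 2 refers back to AIM 1, where the adjustment is for baseline and the examples given are MA and BP levels. AIM 2 speaks of resting BP and MA, not of percentages controlled or adherent. Where the plan does want on-trial covariates, for costs and new comorbidities, it signals this. All of that is fair, and a reader should not infer that the plan certainly conditions on on-trial values. What stands is that the baseline reading needs variables and a time point that are not written, while the phrase that is written names outcomes that do not vary at entry.

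Secondly, one might infer that the plan breaks its intent-to-treat commitment. The documents do not support that. D.8 speaks of the intent-to-treat sample and section 1.a of an intent-to-treat basis, which most directly concern who is analysed. All randomised patients may stay in these models; it is the quantity estimated that changes.

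Thirdly, unadjusted results may exist as well. Aim 2 is powered by a t-test, AIM 1 includes a first set of models with only the dependent variable's baseline, and it analyses 24-hr BP level without this adjustment. That limits the harm, but AIM 2 does not say which model gives its result.

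Fourthly, the numbers are soft. They use a detectable difference as the true effect, correlations from other samples, and a single contrast, whereas AIM 1 names the treatment x time interaction as the test of primary interest. This stands, so I attach no power loss to the planned test.

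**Conclusion.** The concern holds as a conditional one. AIM 2 leaves the timing of two covariates open, and its literal wording points to on-trial values. If those are used, the group coefficient does not estimate the total effect of assignment: 24-hr BP effects are likely to be attenuated, SDT effects are biased and could shrink or reverse, and provider adherence is unclear.

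It is tempting to go further in either direction, by saying that reversal is to be expected or that it is a remote extreme. The documents support neither. The planning figures for MA leave 0.40 or 0.14 SD, while the pilot figures give about −0.37 SD even at the weaker correlation. These are illustrations resting on a linear model and assumed within-arm correlations.

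The two primary outcomes are unaffected. This is worth correcting before analysis, as a matter for the secondary outcomes only.

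**What to change.** In D.10, AIM 2, replace the reference to the primary outcomes with baseline resting SBP and the screening-month MA score, both continuous. Take the clinical and sociodemographic factors at baseline too. Keep the AIM 1 adjustment for the baseline of the dependent variable where one exists (Table 3 lists none for provider adherence). State that this model gives the Aim 2 result. Report any model adjusted for on-trial BP or MA only as exploratory, alongside the mediation analyses already planned in D.10.

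The cost is one or two sentences. The baseline data are already collected, and no stated sample size, alpha or power changes. The only downside is at most one extra exploratory model, if the on-trial question is kept.
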